## Sessions 1-13: TELEREHABILITATION VISITS

**Ensuring Safety During Telerehabilitation Sessions:** At the beginning of each session, all participants will provide emergency information at the start of each telerehabilitation session as per standard tele- practices (i.e., address of current location, current phone number, phone number of emergency contact). The OT study staff will evaluate fall risk prior to beginning the intervention to guide parameters of the in-home telerehabilitation sessions to optimize patient safety.

**Fall Risk Assessment:** At the PRE session, the participant's risk for falling during an OT session will be determined as a combination of their cognitive and physical functioning based on information from established measures and the therapist's assessment/clinical judgment. If a participant is deemed a moderate or high fall risk (based on the stratification below or per the clinician's judgment), additional precautions will be taken to ensure safety. At-risk individuals will have to either 1) have a second person present for Telerehabilitation sessions (e.g., caregiver or trusted friend or family member) to assist with mobility during any dynamic standing activities and/or 2) complete the intervention in a seated position. This second person will be trained by the therapist to provide assistance to the participant during therapy activities that require standing or moving. If the second person is not available, the participant will be required to complete the intervention in a seated position. We will stratify participants into fall risk categories (see Table) using data from the following two measures according to the Table:

- Activities-Specific Balance Confidence (ABC) scale: a self-report questionnaire asking participants to rate their confidence in completing each of 16 activities without losing their balance or becoming unsteady from 0%=no confidence to 100% completely confident. Our risk stratification (see table) uses established cut points for the total ABC score.
- Montreal Cognitive Assessment (MoCA): The MoCA is administered as part of the study's outcome measures. We will use MoCA scores from the PRE assessment to stratify individuals into cognitively impaired (scores  $\leq 23$ ) and non-impaired.

	ABC Scale Score > 80 (High functioning/ confidence in balance)	ABC Scale Score = 50-80 (Moderate functioning/ balance deficits)	ABC Scale Score < 50 (Low functioning/ balance deficits)
MoCA Score 24 – 30 points (Normal cognition / minimal cognitive impairment)	Minimal Fall Risk.	Moderate Fall Risk	Severe Fall Risk
MoCA Score $\leq 23$ points	Moderate Fall Risk	Severe Fall Risk	Severe Fall Risk

(Moderate to severe cognitive impairment)			
---	--	--	--

\*Note that clinician's judgment of fall risk can supersede this stratification scheme. For example, if a participant stratified into the minimal risk category is deemed moderate/severe risk by the clinician's assessment then the above safety precautions will be implemented.

**Cognitive Skills Interest Survey:** We will collect information about participant's interest in the cognitive skills that will be covered during first cognitive rehab-focused visit (session 1) and the perceived usefulness of each cognitive skill at the last cognitive rehab-focused visit (session 4).

**Measurement-based Home Program:** In our past work, we conducted an item response theory Rasch analysis of existing data from n=512 subjects to whom all items of the Fugl-Meyer Upper Extremity Assessment (FMA-UE) had been administered. The analysis identified an item difficulty hierarchy in which items were arranged from easy-to-difficult on a "Keyform Recovery Map". Using a Recovery Map, the specific ability-level of an individual is located relative to items that are too easy, too difficult, or just-right for him/her to accomplish.

The location of the individual on the Recovery Map indicates optimal functional tasks for the client to practice. This is because the FMA-UE items reflect voluntary arm motions, hence the client's ability-level location (relative to item-difficulty) points to optimally difficult functional tasks for which the client has the just-right abilities. Moreover, the Recovery Map defines the functional tasks expected to be accomplished in the short term because they require movements that are slightly above the client's current ability-level. The Map also defines functional tasks expected to be accomplished in the longer term because the functional tasks require movements that are very difficult given the client's current ability-level. Hence, the use of the FMA-UE to define optimally difficult motions and functional tasks is an objective, measurement-based, method to design a home program specific to and personalized for each individual.

To design the measurement-based home program, the tele-FMA-UE will be administered to participants at the initial OT visit (session 4). The participant's ability-level will be located on the Recovery Map according to his/her scores on each item. In a collaborative discussion, the participant and therapist will identify functional tasks that are both optimally difficult (as per the measurement-based Map) and meaningful/motivating to the participant. These tasks will be assigned to the client as his/her home program, i.e., the optimally difficult tasks that the participant will practice in his/her home environment to drive his/her own post-stroke recovery. In this way, the measurement-based Mapping method identifies *what* specific tasks to do at-home. The tele-FMA-UE may be repeated at subsequent OT sessions and post-treatment assessment to monitor progress.

**Cognitive Orientation to Occupational Performance (CO-OP)** is a metacognitive strategy-training approach to teach participants *how* to successfully use the paretic arm for the tasks identified with the measurement-based method described above. CO-OP is emerging as an effective method to improve stroke survivors' skills to self-manage daily life during home and community living tasks. In this approach, with guidance/coaching from an occupational therapist, participants learn to analyze their own performance and develop personalized strategies to overcome task performance challenges with the overall goal of generalizing skills into life situations when a therapist is not present. The CO-OP approach integrates principles of learning theory with motor skill acquisition. The participant is viewed as a "learner" and the therapist is viewed as a "facilitator". The clinician facilitates the participant's guided discovery of

errors and development of cognitive strategies to attain meaningful occupational goals and performance improvements using a “Goal-Plan-Do-Check” framework.

During a CO-OP task-practice session, the participant may be seated or standing at a table with the task objects arrayed within the reachable workspace. The therapist asks the client to identify the task goal (e.g., eating with a spoon), and the client is asked to explain how they plan to approach the activity using guided questions as needed (e.g., explaining movement strategies, set-up of the activity, key performance areas, etc.). The therapist intermittently provides verbal coaching and feedback such as “How do you think it is going?” and/or, “Can you tell me what is going well and what is not going well?” to guide the client through the selected task. Guided-questioning intervals will be adjusted according to patient success with the selected task, allowing the client time to problem-solve independently through errors depending on their level of understanding. Upon completion of the task, the therapist will ask the participant to “Check” their performance, asking questions such as, “How did you do?”, or “Is there anything you want to change the next time you try this task?”. The client will then engage in a discussion about his/her performance on the task according to the goals set prior to the start of the activity, (e.g., “I had trouble keeping my shoulder down while trying to bring the spoon to my mouth.”) The activity will be repeated as necessary to confirm understanding and integration of new strategies.

### Session “POST”: POST-TREATMENT ASSESSMENTS

**Outcome Measures:** We will repeat the same measures administered at pre-treatment to assess cognition (objective and subjective), functional task performance, activity participation, and psychosocial function:

Outcome Domain	Instrument
Cognition	MoCA
Cognition	NeuroQoL-Cognitive Function Short Form v.2.0
Functional Task Performance and Activity Participation	Patient Specific Functional Scale (PSFS)
Functional Task Performance and Activity Participation	Performance Quality Rating Scale (PQRS) a
Functional Task Performance and Activity Participation	Stroke Self Efficacy Questionnaire (SSEQ)
Psychosocial Function	Patient Health Questionnaire (PHQ-9) b
Psychosocial Function	Inventory of Psychosocial Functioning
Psychosocial Function	PROMIS Sleep Disturbance

aThe PQRS will not be administered at the PRE and POST visits and instead will be administered at actual telerehab visits to more proximally assess function. Specifically, it will be administered at the beginning of the first telerehab visit (session 1), the beginning of the first visit with OT (session 5), and at the end of the last telerehab visit (session 13).

bThe Columbia Suicide Severity Rating Scale (C-SSRS) will also be administered if suicidal ideation/intent is endorsed (as described in Section 12.0).

**Telerehab Experience Survey:** At the POST visit, participants will complete two brief surveys regarding their experiences of completing the telerehabilitation program, the Acceptability of Intervention Measure (AIM) and the Intervention Appropriateness Measure (IAM). They will also have the option to provide narrative, qualitative responses about what they liked and did not like about the program. The survey will be administered via Redcap.

## 11.0 Data Management

**Recruitment Data:** Recruitment records will be housed in REDCap. Only IRB-approved study personnel will have access to the REDCap database while actively enrolling for the study.

Data Analysis: Data from the prospective sample (n=20) will be used to calculate descriptive statistics of all outcome measures collected prior to (pre-treatment) and immediately following (post-treatment) the intervention and the corresponding change scores. The preliminary effect sizes of the proposed intervention will be generated by evaluating 1) change in each outcome measure from pre- to post-treatment and 2) the associations between changes in cognitive measures and changes in the participation and psychosocial function measures. To explore the potential additive benefit of cognitive priming, we will compare change in the participation measures between the prospective sample (n=20) and historical data (n=30) from stroke survivors who have completed the telerehabilitation program without the cognitive rehabilitation primer component.

Confidentiality: All data except for the consent forms and HIPPA forms will be coded at the time of data recording. All electronic data will be stored in a password-protected research server that is accessible to IRB-approved study personnel only. All paper data with personally identifiable information (e.g., the consent forms) will be stored in a key-locked cabinet in a key-locked room that is accessible to IRB-approved study personnel only. Other paper data without personally identifiable information including testing sheets documenting testing sequences and notes will also be stored in a cabinet in a key-locked room that is accessible to IRB-approved study personnel only.

Data sharing: Only de-identified coded data will be reported and/or shared with the public and other investigators in publications, in ClinicalTrials.gov, or via data depository.

## **12.0 Provisions to Monitor the Data to Ensure the Safety of Subjects**

The data and safety monitoring plan will include an internal Data Safety Monitoring Committee (DSMC) and the Institutional IRB. The purpose of the DSMC and IRB are to ensure the safety of participants and the validity and integrity of the data.

Data Safety Monitoring Committee (DSMC). The internal DSMC will consist of the PI and Co-Investigators on the proposal. The functions of the DSMC will include: 1) providing scientific oversight; 2) reviewing all adverse effects or complications related to the study; 3) monitoring enrollment; 4) reviewing summary reports relating to compliance with protocol requirements; and 5) providing advice on resource allocation. The DSMC will meet quarterly, remotely or in-person. The recommendations of the DSMC will be reviewed and the PI will take appropriate corrective actions as needed.

Reporting of safety data: All serious adverse events will be reported to the IRB as they occur. Summative safety data will be reported to ClinicalTrials.gov and in publications. As such, we will register this study in ClinicalTrials.gov as soon as the study commences and report results including all adverse events as soon as the study is completed following the guidelines. To protect participants' confidentiality, personally identifiable information will not be used for reporting. Only de-identified or aggregated data will be used for reporting.

PHI: Study participants will receive a study-specific ID code. All study information will utilize only the study ID code, not PHI. PHI will be stored in a password protected site on the MUSC network. The master list that links the study ID to PHI will be stored separately from other study data in a password protected site on the MUSC network to minimize the potential for loss of confidentiality

if study documents are lost or compromised. Paper-copy PHI data will be stored in a locked storage cabinet within a locked office.

**Suicidal Intent:** Suicidal intent will be assessed during the pre-treatment and post-treatment assessment visits via item 9 of the PHQ-9 (“Thoughts that you would be better off dead, or of hurting yourself”). Participants who endorse a rating  $> 0$  (“not at all”) on this item and verbally endorse suicidal ideation upon query will then be assessed using the Columbia Suicide Severity Rating Scale (C-SSRS). The research team is comprised of licensed, experienced occupational therapists and clinical psychologists, all of whom will have training in suicide risk assessment. Consistent with the triage points determined by the scale authors, any positive endorsement to items 3 – 6 on the C-SSRS will necessitate completion of a safety plan (which will be sent to them via email once completed) and consultation with the PI or a designated clinician Co-Investigator ([name]). Any positive endorsement of items 4 – 6, and participation may be discontinued based on clinician Co-I judgment. Depending upon the follow-up to endorsement of item 3 (passive ideation), participation may also be discontinued. Any participant endorsing items 4-6 will be referred to immediate consultation with the PI or a designated clinician Co-Investigator ([name]) who will discuss a safety plan and provided appropriate referrals and follow-up contact to facilitate engagement in care. In the case of imminent suicidal intent or danger, a research team member will remain in contact with the participant while calling 911 (providing the dispatch with the participant’s current location). A research team member will also contact the participant’s emergency contact.

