### **14.0 Risks to Subjects**

There is a minor risk of mental and/or physical fatigue from engaging in the cognitive rehabilitation and occupational therapy rehabilitation intervention. There is also a risk of falling during the occupational therapy sessions. There is a risk that stroke survivors may experience sadness, fear, or anger if they have difficulty with the assessments or intervention because they may develop a greater realization of their deficits. It is also possible that the task-practice sessions result in temporary muscle soreness or fatigue. These risks to participants are no more than a usual-care stroke rehabilitation assessment and/or intervention session.

There is a risk of a loss of confidentiality of personal information that is used in this study although researchers will take appropriate steps to protect any information collected about the participants.

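### The plan promises to report all adverse events but lists no inquiry that would find non-serious ones outside the therapist's view, so the count is likely to be incomplete

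*Combined protocol and SAP*

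**What the plan says.** Section 12.0 says the investigators will register the study and "report results including all adverse events as soon as the study is completed". That promise is not limited to serious or related events. The same section says "All serious adverse events will be reported to the IRB as they occur", and gives the committee the function of "reviewing all adverse effects or complications related to the study". On membership it states: "The internal DSMC will consist of the PI and Co-Investigators on the proposal".

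Section 14.0 names mental and physical fatigue, muscle soreness and emotional distress as risks, and adds: "There is also a risk of falling during the occupational therapy sessions".

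In Section 10.0, under Sessions 1-13, the home program is described as "the optimally difficult tasks that the participant will practice in his/her home environment". The endpoint table in Section 4.0 calls such practice self-directed. The safety routine under the same Section 10.0 heading says that "all participants will provide emergency information at the start of each telerehabilitation session"; the items it lists are current address, phone number and emergency contact.

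**The concern.** A promise to report every adverse event needs a way of finding them. If nobody asks, the count measures what participants mention unprompted and what therapists happen to see. The exposure outside the therapist's view is home practice, which is also where nothing is asked.

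Unprompted reporting may be weak in this population. Section 2.0 cites persistent cognitive impairment in about 70% of stroke survivors, commonly in attention and executive function, and aphasia below the exclusion threshold is permitted. A low published count could then be taken as reassurance about remote therapy with home practice, and the committee could not act on a fall it never heard about.

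**Working it through.** This is mainly a check of the text. The plan states no adverse-event rate, so there is no figure of its own to reproduce.

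**Step 1: every contact.** The schedule gives 1 PRE + 5 × 2 + 3 × 1 sessions + 1 POST = 15 visits, which agrees with Section 10.0. What each is said to contain:

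- PRE: consent, emergency contact, characterization and outcome measures, fall-risk stratification, technology training, introduction to the approaches. Pain is recorded here to describe the sample and is not among the POST measures.
- Start of each of the 13 sessions: emergency information only.
- Within sessions: therapy content. The CO-OP check questions concern task performance, not harm.
- POST: outcome measures, two surveys on acceptability and appropriateness, and an optional narrative on likes and dislikes.
- Fall risk: stratified at PRE, with no later count of falls.
- Section 11.0, Data Analysis: outcome measures only, with no adverse-event summary.

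No definition, grading, relatedness rule, collection window or form for adverse events is given.

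**Step 2: what is solicited.** The PHQ-9 at PRE and POST asks about low mood, fatigue and suicidality over the last two weeks, and Section 12.0 sets out an escalation path for suicidality. It does not cover falls, injury or soreness. The home program is developed at the end of session 4 (week 3) and sessions run to week 9, so home practice can span about six weeks. The POST questionnaire looks back over two.

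**Step 3: what 20 participants can show.** With complete capture and no events, the one-sided 95% upper bound is 1 − 0.05^(1/20) = 13.9%; the upper limit of the two-sided 95% interval is 1 − 0.025^(1/20) = 16.8%. With incomplete capture, these bounds describe the rate of volunteered or observed events, not the true rate.

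**Step 4: illustration under assumed values.** Neither the true rate p nor the capture share c is in the documents. The chance that none of 20 participants is counted as having the event is (1 − p × c)^20:

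| Assumed true rate | c = 100% | c = 75% | c = 50% | c = 25% |
|---|---|---|---|---|
| 10% | 12.2% | 21.0% | 35.8% | 60.3% |
| 20% | 1.2% | 3.9% | 12.2% | 35.8% |
| 30% | 0.1% | 0.6% | 3.9% | 21.0% |

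At a true rate of 20%, the expected number counted falls from 20 × 0.20 = 4 with full capture to 20 × 0.20 × 0.50 = 2 at half capture.

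**The case against.** The strongest reply is proportionality. This is a 20-person, single-group behavioural pilot with no safety endpoint and no between-arm safety comparison to bias. Section 14.0 rates its risks as no greater than usual-care stroke rehabilitation, and each participant has 13 live contacts with a therapist who may well ask. Section 14.0 also ties falls and soreness to sessions, where a therapist is watching and at-risk participants have a second person present or are seated. These points lower the stakes. They do not close the gap: informal asking without a form gives no consistent count, soreness from a session can appear after the call, and home practice is assigned.

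Several stronger readings are tempting but are not supported:

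- That no visit asks about any harm. The PHQ-9 items are an exception.
- That the committee reviews only related events, already judged so by the investigators. The list says its functions will include this review; the word only is absent, the relatedness phrase may attach to complications alone, and no prior relatedness judgement is described. Serious events reach the IRB without that limit.
- That most practice is unsupervised. Home practice is assigned, but its amount is not stated.
- That participants cannot be expected to report events. No eligibility criterion requires cognitive impairment, and people without decisional capacity are excluded.
- That safety rates from this pilot will feed the larger trials. Section 1.0 says this of effect estimates only.

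**Conclusion.** The concern holds in a limited form. The listed procedures cannot be relied on to deliver the count that Section 12.0 promises. Non-serious events outside the therapist's view, especially falls and soreness in home practice, would be recorded only if volunteered, so the count is likely to be incomplete. A reader might go further and say that harm is understated by a known amount. The direction is plausible, but the size cannot be derived from the documents, and the capture shares in the table are assumptions.

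The 13.9% bound is firm, given complete capture in all 20 participants. Under-capture weakens what this sample can say about safety without removing it. The committee's wording is a secondary point: it can be read as narrower than the reporting promise and should be aligned with it. The conclusion assumes that no separate procedure, outside the documents reviewed, already elicits adverse events.

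**What to change.** Add a short fixed inquiry to the existing start-of-session safety check and to POST, covering the time since last contact: any fall, injury, new pain or soreness, marked fatigue, distress, emergency visit or hospital stay. Record each positive answer in REDCap with its date, its setting (session, home practice or elsewhere) and relatedness as a separate field. Reword the committee's function in Section 12.0 so that it reviews all recorded events. Add a line to Section 11.0 for a descriptive summary of participants with events and numbers of events, with exact intervals.

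The cost is 1-2 minutes at each of 13 + 1 = 14 contacts, or 14-28 minutes per participant over the whole study, plus one form. No extra visit or staff is needed. The drawback is a higher reported event count, which should be presented as the result of systematic asking.
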